17.1 Study Estimands

Primary Estimand

The primary estimand construction elements are:

- Treatment of interest: The initially randomized treatment Group 1 (edaravone daily) to be compared with Group 2 (edaravone on/off) for up to 96 weeks.
- Population: Subjects with ALS as defined in the analysis set.
- Variable: Time from the randomization date in Study MT-1186-A02 to at least a 12-point decrease in ALSFRS-R or death, whichever happens first.
- Inter-current event (ICE) handling strategy
 - > ICE1 Additional AMX0035 treatment up to 96 weeks double-blind treatment period will be handled using treatment policy strategy.

- ➤ ICE2 Death will be handled within the primary endpoint derivation using composite variable strategy.
- Population-level summary: The Kaplan-Meier estimates and the hazard ratio between Group 1 and Group 2 will be derived from Kaplan-Meier plot and Cox PH regression, respectively.

The treatment effect on the primary endpoint taking death event (ICE2) into account is attributed regardless of the use of additional AMX0035 treatment (ICE1).

Secondary Estimand

The secondary estimand will be tested as supportive analysis for the primary endpoint.

The secondary estimand construction elements are:

- Treatment of interest: as specified for the primary estimand.
- Population: as specified for the primary estimand.
- Variable: as specified for the primary estimand.
- ICE handling strategy
 - > ICE1 Additional AMX0035 treatment up to 96 weeks double-blind treatment period will be handled using hypothetical strategy.
 - > ICE2 Death will be handled within the primary endpoint derivation using composite variable strategy.
- Population-level summary: as specified for the primary estimand.

The above estimand will also be tested when the primary endpoint event is censored if it occurs after ICE1 (additional AMX0035 treatment). In this estimand, the treatment effect will be attributed as if AMX0035 treatment had not been available.

17.2 Determination of Sample Size

The sample size for this study is not based on a formal statistical calculation. In total, approximately 300 subjects who have successfully completed Study MT-1186-A02 will be enrolled in this study. However, data from 380 subjects (190 subjects per group) randomized in Study MT-1186-A02 will be included for all analysis. Using Study MT-1186-A02 and MT-1186-A04 survival data, the planned sample size of 190 subjects per group initially randomized in Study MT-1186-A02 will have 70% power to detect a statistically significant result if the true hazard ratio between edaravone 105 mg daily (test) and edaravone 105 mg on/off regimen (control) in the primary endpoint is 0.775, which means 22.5% risk reduction in the hazard due to daily treatment, assuming 65% survival rate at Week 48 for the control group. This calculation of 70% power assumes a 2-sided alpha of 20% based on a rare disease condition, 19 using the log-rank test and a follow-up time of up to 48 weeks in Study MT-1186-A04.

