1 PROTOCOL SYNOPSIS

Name of Company Mitsubishi Tanabe P Corporation Name of Finished Pr Edaravone (MT-1186) Name of Active Ingree Edaravone (MT-1186) (3-methyl-1-phenyl-2-	oduct edient	Individual Study Table Referring to Module 5 of the CTD Volume: Page:	(For National Authority Use Only)
Study Protocol Title of Study	MT-1186-A04 A Phase 3b, Multicenter, Randomized, Double-blind Extension Study to Evaluate the Continued Efficacy and Safety of Oral Edaravone Administered for an Additional Period of up to 48 Weeks Following Study MT-1186-A02 in Subjects with Amyotrophic Lateral Sclerosis (ALS)		
Study Centers Study Period	Multicenter study Estimated date first subject enrolled: January 2022 Estimated date last subject completed: TBD		
Phase Objectives	Primary Objective: To evaluate and compare the efficacy of the following		
	 2 dosing regimens of oral edaravone in subjects with amyotrophic lateral sclerosis (ALS), based on the time from the randomization date in Study MT-1186-A02 to at least a 12-point decrease in Revised ALS Functional Rating Score (ALSFRS-R) or death, whichever happens first, over the course of the study or until oral edaravone is commercially available in that country: Oral edaravone 105 mg administered once daily Oral edaravone 105 mg administered for 10 days followed by placebo for 18 days (regimen denoted as 		
	on/off). Secondary Objective: • To evaluate the safety and tolerability of oral edaravone at a dose of 105 mg once daily compared to oral edaravone at a dose of 105 mg including placebo (regimen denoted as on/off) in subjects with ALS over the course of the study or		

Name of Company Mitsubishi Tanabe P Corporation	harma	Individual Study Table Referring to Module 5 of the CTD	(For National Authority Use Only)
Name of Finished Pro	oduct	CID	
Edaravone (MT-1186)		Volume:	
Name of Active Ingre	edient		
Edaravone (MT-1186) (3-methyl-1-phenyl-2-		Page:	
	until oral e country.	daravone is commer	cially available in that

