Edaravone (MT-1186, MCI-186), developed by Mitsubishi Tanabe Pharma Corporation, is a free radical scavenger that reduces oxidative stress and slows the progression of ALS as estimated by the Revised ALS Functional Rating Scale (ALSFRS-R). The clinical development program was designed to evaluate functional changes in ALS versus placebo up to 24 weeks. The concomitant use of riluzole was permitted in both edaravone and placebo groups. Efficacy of edaravone has been demonstrated in definite or probable subjects with ALS diagnosed with El Escorial criteria. 9,10,11,12 Higher relative quality of life has been demonstrated in subjects receiving edaravone compared to the placebo group, and these differences were maintained up to 48 weeks. 13 Evidence regarding the delay of some of the definite disease progression events (including death, disability of independent ambulation, loss of upper limb function, tracheotomy, use of respirator, use of tube feeding, and loss of useful speech) was also found at 48 weeks. 13 During the edaravone clinical development program, all fatal events, which occurred after respiratory failure, pneumonia or cardiac arrest, or serious adverse events (SAEs) such as gastrointestinal or respiratory disorders, were attributed or suspected to be attributed to disease progression. However, higher incidence of contusion, gait disturbance, headache, eczema, contact dermatitis, and glucosuria was reported in the edaravone group.¹⁴ Most of the population of the clinical development

program of edaravone was Japanese. However, a pharmacokinetic (PK) analysis compared Japanese and Caucasian populations, and no differences were observed between them. 15

In 2015, edaravone was approved in Japan and South Korea (as Radicut®) as a therapeutic option to slow down the progression of the disease in subjects with ALS. This was followed by approval (as Radicava®) by the US FDA in 2017 and the Health Canada (as RadicavaTM) in 2018. It was approved in Switzerland and China in 2019, Indonesia in 2020, and Thailand in 2021.

Edaravone oral suspension for the treatment of ALS was approved in the United States in May 2022 under the trade name RADICAVA ORS®.

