8 STUDY DESIGN

8.1 Overall Study Design

This is a Phase 3b, multicenter, double-blind, parallel group, randomized extension study that will evaluate the efficacy and safety of 2 treatment regimens of edaravone for an additional period of up to 48 weeks following Study MT-1186-A02 in subjects with ALS as follows:

- Group 1: Oral edaravone 105 mg dose once daily in each 28-day cycle for up to 48 weeks or until the drug is commercially available in that country.
- Group 2: Oral edaravone 105 mg dose for 10 days followed by 18-day placebo (regimen denoted as on/off) in each 28-day cycle for up to 48 weeks or until the drug is commercially available in that country.

Subjects who meet study MT-1186-A04 eligibility criteria, will continue in the same treatment group/regimen that they were in during Study MT-1186-A02.

A schedule of assessment of all study procedures is provided in Table 1.

The Week 48 study procedures from Study MT-1186-A02 will be used as the screening/entry criteria for Study MT-1186-A04, followed by a treatment period of up to an additional 48 weeks or until oral edaravone is commercially available in each country, whichever time period is shorter, and a safety follow-up period of 2 weeks.

During the conduct of Study MT-1186-A04, the dose of edaravone may be adjusted or the study may be stopped based on the interim futility or final analyses performed for Study MT-1186-A02, taking into consideration the benefit and risk balance. However, unless any significant safety issue is found based on these 2 analyses, the same regimen will be kept while maintaining the blind conditions for all site-facing personnel and all personnel directly involved with the conduct of the study.

Concomitant use of riluzole is permitted throughout the course of the study when the dose and regimen remain unchanged from the screening visit evaluation of ALSFRS-R of Study MT-1186-A02 through the end-of-treatment (EOT) or early termination (ET) of Study MT-1186-A04. Dose reduction, dose interruption, or discontinuation due to the onset of AEs, progression of dysphagia, or gastrostomy while on oral edaravone 105 mg are allowed. The use of AMX0035 will be allowed for patients in the event that it becomes commercially available via prescription in their respective country. AMX0035 should be taken at least 1 hour after MT-1186/oral edaravone dosing.

EOT assessments will occur at Week 48 (Visit 5).

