10.1.5 End-of-Study Options

The EOT visit will occur at either Week 48, when the drug is commercially available in that country, if results from Study MT-1186-A02 dictate, or in the event the Sponsor discontinues the study.

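### The 70% power assumes complete follow-up to 96 weeks and allows nothing for the stop at commercial availability, which the protocol's own dates made foreseeable in the US

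*Protocol*

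**What the plan says.** Protocol 17.2, repeated in the synopsis and in substance in SAP 4.2, says that "the planned sample size of 190 subjects per group initially randomized in Study MT-1186-A02 will have 70% power" if the true hazard ratio "in the primary endpoint is 0.775, which means 22.5% risk reduction in the hazard due to daily treatment". The control group is assumed 65% event-free at Week 48; SAP 4.2 repeats the 65% without the time point. Further: "This calculation of 70% power assumes a 2-sided alpha of 20"%, "using the log-rank test and a follow-up time of up to 48 weeks in Study MT-1186-A04". No allowance for dropout or shortened follow-up is described.

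The follow-up rule is elsewhere. Protocol 8.1 gives a treatment period of up to 48 more weeks "or until oral edaravone is commercially available in each country, whichever time period is shorter", then two weeks of safety follow-up. Protocol 10.1.5 agrees: "The EOT visit will occur at either Week 48, when the drug is commercially available in that country", among other triggers. Table 1 schedules no ALSFRS-R after the end-of-treatment visit. Under 17.4.5.1, subjects without an event are right censored at their last study visit.

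On timing, section 6.1 states: "Edaravone oral suspension for the treatment of ALS was approved in the United States in May 2022". The synopsis gives "Estimated date first subject enrolled: January 2022". SAP Table 2 lists the United States among seven participating countries, without numbers per country.

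**The concern.** The power statement and the stopping rule describe different amounts of follow-up. The first relies on 96 weeks from A02 randomisation. The second can end a country's contribution at any point after A04 Day 1, and it also stops collection of the ALSFRS-R, which supplies the 12-point component of the primary endpoint. The protocol version that carries the 70% already records approval in one participating country.

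Two things are at stake. The stated power would be somewhat too high. And late Kaplan-Meier information would come mainly from countries where the product is not yet marketed, although the estimand covers all randomised subjects for up to 96 weeks.

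**Working it through.** Weeks are counted from A02 randomisation unless marked A04.

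**Inputs (protocol 17.2).** 190 per arm; HR 0.775; control 65% event-free at Week 48; two-sided alpha 0.20 (z = 1.2816). Added assumptions: constant hazards and no dropout, chosen because they reproduce the stated figure.

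**Formulas.** Control S(t) = 0.65^(t/48); daily arm S(t)^0.775. Expected events d = 190 × [(1 − S_control) + (1 − S_daily)]. Power = Φ(|ln 0.775| × √(d/4) − 1.2816), plus an opposite tail of 0.1 to 0.4 points. |ln 0.775| = 0.2549.

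**Events needed for 70%.** 4 × (1.2816 + 0.5244)² / 0.2549² ≈ 201 (Schoenfeld). Freedman's formula gives 203.

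**Reproducing the 70%.** At Week 96, control S = 0.4225 and daily S = 0.5129. Events are 109.7 + 92.6 = 202.3. Then 0.2549 × √(202.3/4) = 1.813, and power is 70.3% (69.9% by Freedman). The plan's figure is reproduced with almost no slack.

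**Readings that do not reproduce it.** Everyone stopped at Week 48: 66.5 + 53.9 = 120.4 events, power 55.0%. Taking 65% as the Week 96 rate gives the same 120.4 events and 55.0%.

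**Timing.** January 2022 plus 48 weeks falls between 3 December 2022 and 2 January 2023, about seven months (six to eight) after May 2022.

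**Effect of shorter US follow-up.** The US share f is assumed. Events = f × d(cut) + (1 − f) × 202.3, with d(48) = 120.4 and d(72) = 165.3. For f = 30% and a Week 48 cut: 0.3 × 120.4 + 0.7 × 202.3 = 177.7.

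| US share (assumed) | Events, US cut at Week 48 | Power | Events, US averaging 72 weeks | Power |
|---|---|---|---|---|
| 10% | 194.1 | 69.0% | 198.6 | 69.8% |
| 20% | 185.9 | 67.7% | 194.9 | 69.2% |
| 30% | 177.7 | 66.3% | 191.2 | 68.6% |
| 40% | 169.5 | 64.9% | 187.5 | 68.0% |
| 50% | 161.4 | 63.4% | 183.8 | 67.4% |

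The Week 48 column is the severest case, with no A04 time from any US subject. The 72-week column treats all US subjects as followed for exactly 72 weeks. An equal split over seven countries (14%) gives 68.5% and 69.5%.

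**Would continued follow-up after study drug recover the power?** Take 30% US and suppose the arms converge fully (HR 1) after Week 48. Extra events: 0.3 × 190 × (0.650 + 0.716) × 0.35 = 27.3, making 205.0 in all. The average log hazard ratio shrinks to 0.2549 × 177.7/205.0 = 0.2210. Power is 62.0%, against 66.3% with plain censoring.

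**The case against.** The strongest reply is that the 70% drives no decision. Protocol 17.2 opens by saying the sample size rests on no formal calculation, since the number was fixed by A02. Section 17.4.5.7 disclaims a formal hypothesis and control of type I error. The limit is also disclosed: the primary objective is bounded by commercial availability, and both the estimand and the power text speak of periods of up to a stated length. Stopping by country is administrative, and region is a log-rank stratum and a Cox covariate, so the main cost is precision and there is no evident bias in the treatment comparison. This stands, and it keeps the point modest. It does not make 70% the power under the protocol's own rule.

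A reader might go further and infer that US subjects could not supply 96 weeks at all. The documents do not support that. The trigger is commercial availability; they record only approval, and the January 2022 start is an estimate. US subjects also contribute all their A02 time and any A04 time before availability.

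A reader might also infer that vital status is lost after such a stop. Protocol 9.6 and 12.2.2 require event calls after a subject drops out or discontinues. Whether that covers an availability-triggered end of treatment is unclear, so this is an ambiguity and not a demonstrated loss. The calls do not cover ALSFRS-R in any case.

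Finally, the SAP reports that A04 was terminated after the A02 futility analysis and that no final analysis will be done. That removes most of the practical consequence, but the stated figure remains in both documents.

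**Conclusion.** The concern holds in a limited form. The 70% is the power under complete follow-up to 96 weeks, so it is the most the stated assumptions can give. The protocol's country rule can only lower it, and on the protocol's own dates shorter US follow-up was foreseeable, though not certain. No allowance is stated.

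The loss is about 0.6 to 6.9 points for assumed US shares of 10% to 50%, and about 0.8 to 1.8 points at an equal split over seven countries. This rests on constant hazards, no dropout, and an assumed US share and cut time. The 55% figure would need every subject in every country to stop at Week 48, and nothing in the documents suggests that. The point is separate from how many A02 completers entered A04.

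**What to change.** In protocol 17.2, the synopsis and SAP 4.2, state that 70% is the maximum, reached only if every randomised subject is followed to an event or to 96 weeks. Beside it, give the power under the country-availability rule, using the sponsor's actual US share and expected availability date, with a range such as the table above. SAP 4.2 should also restore the time point for the 65%.

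The cost is a few sentences and a slightly less favourable stated power. The treatment rule itself is not in question.

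Continuing telephone ALSFRS-R and vital-status follow-up after an availability-triggered end of treatment is an optional choice of estimand, not a required correction. It would serve a treatment-policy question, but it could dilute the contrast and cost more power than plain censoring, as the last step of the working shows.

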17.3 Analysis Sets

The statistical analysis will be based on separate analysis sets, defined as follows:

Randomized Set:

The randomized set is defined as all of the subjects randomized in Study MT-1186-A02. The subjects will be grouped by the planned treatment allocation (as randomized).

Efficacy Analysis Set:

The full analysis set (FAS) is defined as all of the subjects randomized in Study MT-1186-A02 who received at least 1 dose of study medication in Study MT-1186-A02 and had any efficacy data collected after randomization. Subjects in the FAS will be grouped and analyzed based on the planned treatment allocated (as randomized). Efficacy endpoints will be analyzed using the FAS.

Safety Analysis Set:

The Safety Analyses Set (SAF) is defined as all of the subjects randomized in Study MT-1186-A02, and who received at least 1 dose of study drug in Study MT-1186-A02. Subjects will be grouped and analyzed based on the actual treatment received. Safety endpoints will be analyzed using the SAF by treatment group.

17.4 Statistical Analyses

17.4.1 General Considerations

The statistical analysis will be performed using SAS® Version 9.4 or higher.

In general, continuous variables will be summarized descriptively using the number of observations (n), mean, standard deviation, median, minimum, and maximum. Categorical variables will be summarized using frequency counts and percentages.

Statistical summaries will be presented for the changes from baseline to each visit for the primary, secondary (key and other), and exploratory endpoints that are applicable.

All individual subject data will be listed.

17.4.2 Data Handling

17.4.2.1 Definition of Baseline for the Efficacy and Safety Endpoints

The data collected before the first study drug dose administration date in Study MT-1186-A02 will be used as the baseline for statistical analysis in Study MT-1186-A04.

17.4.2.2 Handling of Time Point Data in Analyses Performed by Measurement Time Point (Analysis Visit Windows)

For the analyses performed for each measurement time point, the allowable range of data handling for the analysis will be specified as analysis visit window in the SAP.

No data imputation will be performed using data from outside the allowable range. If multiple values are available within the allowable range for the endpoint in question, then the latest value will be analyzed.

17.4.2.3 Handling of Reference Values and Indeterminate Values for Clinical Laboratory Test Parameters

If a laboratory test value or its reference is indeterminate due to a problem with the test sample, then this value will be handled as a missing value.

17.4.3 Statistical Analysis Method

17.4.3.1 Subject Disposition

The following will be provided:

- The total number of screened subjects: defined as those who met the inclusion criteria regarding the target indication and signed the ICF
- The total number of subjects enrolled
- The total number (%) of subjects in each analysis set
- The total number (%) of subjects who completed Week 48
- The total number (%) of subjects who discontinued the study, and the reasons for discontinuation

17.4.3.2 Concomitant Medications

All concomitant medications will be coded using the WHO DD and anatomical therapeutic chemical (ATC) system. Concomitant medication is defined as any medication, other than study drug, which is taken after the first dose administration in Study MT-1186-A02. Concomitant medications, except for riluzole, will be summarized by ATC level 2 categories and preferred name.

Riluzole and AMX0035 administration will be summarized separately.

17.4.4 Study Medication Exposure

The duration of exposure in days will be calculated as follows:

Date of last dose of edaravone in Study MT-1186-A04 – date of first dose of edaravone in Study MT-1186-A02 + 1

If the date of first dose or the date of last dose cannot be determined, the duration calculation will not be completed. The duration of exposure will be summarized using descriptive statistics.

All exposure data will be listed. Interruptions and compliance are not considered for the duration of exposure.

17.4.5 Efficacy Analysis

17.4.5.1 Primary Efficacy Analysis

Data of time from randomization in Study MT-1186-A02 to at least a 12-point decrease in ALSFRS-R or death will be included regardless of AMX0035 use (ICE1). In other words, data following AMX0035 treatment will be used in the analysis and will not be censored.

The primary efficacy endpoints associated with the study estimand will be analyzed on the randomized set using Kaplan-Meier estimates, 2-sided alpha with a nominal 20% significance level and 80% CIs. The comparison between Treatment Group 2 versus Treatment Group 1 will be performed using a log rank test with Study MT-1186-A02 randomization strata of ALSFRS-R rate of decline score from the MT-1186-A02 screening period (2 levels strata of -1,-2 or -3,-4) and the geographical region (3 levels strata of Europe, America, or Asia Pacific). Subjects without events during treatment will be right censored at the date of last study visit.

17.4.5.2 Supportive Analyses for the Primary Efficacy Endpoint

The primary efficacy endpoint will also be analyzed using the Cox Proportional Hazard (COX PH) Model with terms for treatment as explanatory variable and baseline ALSFRS-R score, and the MT-1186-A02 randomization strata as covariates. This statistical test will be done as 2-sided with a nominal 20% significance level. Point estimates of treatment differences will be accompanied with 2-sided 80% CIs.

17.4.5.3 Supportive Analysis for the Secondary Estimand

The primary analysis will be repeated when the event of interest is censored if it occurs after initiation of AMX0035 treatment, using the Inverse Probability of Censoring Weighting (IPCW by Robins JM, Finkelstein et all, 2000)²⁰ to adjust for non-random time-dependent covariates. Further details on this supportive analysis will be specified in the Statistical Analysis Plan.

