3.2.2. Secondary Estimand

The secondary estimand will be tested as supportive analysis for the primary endpoint.

The secondary estimand construction elements are:

- Treatment of interest: as specified for the primary estimand.
- Population: as specified for the primary estimand.
- Variable: as specified for the primary estimand.
- ICE handling strategy
 - ➤ ICE1 Additional AMX0035 treatment up to 96 weeks double-blind treatment period will be handled using hypothetical strategy.
 - ➤ ICE2 Death will be handled within the primary endpoint derivation using composite variable strategy.
- Population-level summary: as specified for the primary estimand.

The above estimand will also be tested when the primary endpoint event is censored if it occurs after ICE1 (Additional AMX0035 treatment). In this estimand, the treatment effect will be attributed as if AMX0035 treatment had not been available.

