8.3.2. Efficacy Measures

8.3.2.1. Time to 12-point decrease in ALSFRS-R or death

The primary end point in this study is the time from the randomization date in Study MT-1186-A02 to the first occurrence of at least 12-points decrease in ALSFRS-R or death, whichever happens first.

ALSFRS-R is a questionnaire used to measure the impact of ALS that is evaluated by the Investigator. The scale measures the subjects' physical function across 12 activities of daily living. The date of the evaluation along with the results will be recorded on the eCRF with respect to "4 Handwriting" and "5 eating motion," the results for the dominant hand (the hand used in daily life at the time of screening) will be recorded.

- ALSFRS-R total score for each visit will be derived from the sum of 12 items². For the item 5 "Eating disorder," either the item (a) or (b) will be selected corresponding to subjects with or without gastrostomy respectively. The maximum total score is 4 x 12=48.
- ALSFRS-R domains Score. The following subdomain will be calculated for each visit as well as the change from baseline to week 48.
 - O Bulbar function = total of items 1 to 3
 - O Limb function = total of items 4 to 9
 - o Fine motor function = total of items 4 to 6
 - O Gross motor function = total of items 7 to 9
 - o Respiratory function = total of items 10 to 12

The time to event variable will be calculated as follows:

Time to event=Event Date or Last Observed Date – Randomization Date + 1

- The time to the first occurrence of at least 12-point decrease in total ALSFRS-R score will be calculated from randomization date in MT-1186-A02 until last total ALSFRS-R score measurement available during MT-1186-A04. If the first occurrence of at least a 12-point decrease at any visit time point is observed, then the time variable will be calculated as the difference between the date that ALSFRS-R score was observed for which the above decreased occurred and the randomization date in MT-1186-A02.
- In case of death, the time variable will be calculated as the difference between death

² Refer to Appendix I of the protocol.

Mitsubishi Tanabe Pharma America, Inc.

date and the randomization date in MT-1186-A02.

• In case the subject did not experience either of the above events, the time variable will be calculated as the difference between date of the last observed date (Censored date) and the randomization date in MT-1186-A02.

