9.2.1.3. Additional Supportive Analyses Addressing the Secondary Estimand				
_				
"				
			_	

Statistical Analysis Plan
Study No. MT-1186-A04

Mitsubishi Tanabe Pharma America, Inc.

[figure not shown]

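### As worded, the secondary-estimand rule censors only events after AMX0035 start and leaves event-free starters at risk, so censoring depends on the outcome

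*Protocol*

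**What the plan says.** The secondary estimand treats AMX0035 use with a hypothetical strategy. Protocol 17.1 gives the target: "the treatment effect will be attributed as if AMX0035 treatment had not been available". Its population-level summaries are those of the primary estimand, namely Kaplan-Meier estimates and the Cox hazard ratio.

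The censoring rule is worded in terms of the event. SAP 3.2.2, in words shared with Protocol 17.1, says "The above estimand will also be tested when the primary endpoint event is censored if it occurs after ICE1". Protocol 17.4.5.3 says "The primary analysis will be repeated when the event of interest is censored if it occurs after initiation of AMX0035 treatment", with adjustment "using the Inverse Probability of Censoring Weighting". Neither document, as far as it can be read, gives the date at which such a subject is censored.

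The analysis to be repeated has its own rule for everyone else. Protocol 17.4.5.1: "Subjects without events during treatment will be right censored at the date of last study visit". SAP 8.3.2.1: "In case the subject did not experience either of the above events, the time variable will be calculated as the difference" between the last observed date and the randomization date. Neither makes an exception for AMX0035 starters.

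Protocol 17.4.5.3 defers the detail: "Further details on this supportive analysis will be specified in the Statistical Analysis Plan". The SAP has a section for it, 9.2.1.3, headed "Additional Supportive Analyses Addressing the Secondary Estimand", but its body cannot be read in the public copy.

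**The concern.** Put the two rules together and follow two subjects who both start AMX0035 at Week 50. One reaches the 12-point decline at Week 70: that event is removed. The other stays event-free: under the last-visit rule, this subject stays in the risk set to the end. After starting AMX0035, subjects can contribute event-free time but never an event, so their observed hazard is zero.

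IPCW corrects censoring that can be explained by covariates measured before the censoring happens. Here the censoring is set off by the event itself, and no covariate history makes that ignorable. The method fits the target only if every starter leaves the risk set at initiation and the weights model initiation.

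At stake are the Kaplan-Meier curves for a world without AMX0035, which the estimand names as an output and which would be too high in both arms. The hazard ratio is also at stake if uptake differs between arms. SAP 5.2 cancels the final analysis, so the interim analysis in SAP 5.1 is the only planned run.

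**Working it through.** **The plan's own figure.** Inputs from Protocol 17.2: 190 per group, hazard ratio 0.775, 65% event-free at Week 48 in controls, two-sided alpha 20%. With exponential times and 96 weeks of follow-up, control event-free = 0.65² = 0.4225; daily = 0.4225^0.775 = 0.5129; events = 190 × (2 − 0.4225 − 0.5129) = 202.3. Schoenfeld power = Φ(√202.3 × |ln 0.775| / 2 − 1.2816) = Φ(0.531) = 70.2%. The stated 70% reproduces, and the censoring rule does not touch it. The same event rate is used below.

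**Simple case: no confounding, no AMX0035 effect.** Assumptions not in the documents: a fraction u of subjects would start AMX0035, at a time uniform over Weeks 24 to 96, unrelated to prognosis. By week t the fraction started is G(t) = u(t − 24)/72 for t > 24, and zero before. The control hazard is h = −ln(0.65)/48 per week.

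*Literal rule, late event censored at its own date.* Everyone still event-free is at risk, but only non-starters can have a counted event. The observed hazard is h(1 − G(t)). Integrated to Week 96 it is h(96 − 36u), so the Kaplan-Meier curve tends to 0.65^(2 − 0.75u).

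*Literal rule, late event moved back to the start date.* The observed hazard is h·S(t)(1 − G) / [S(t)(1 − G) + G·S(96)], where S is the true event-free curve; this was integrated numerically.

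*Every starter censored at start.* Starting is independent of the event here, so the curve tends to 0.4225.

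| u | Truth | Censored at event date | Moved back to start | Excess (points) |
|---|---|---|---|---|
| 20% | 42.3% | 45.1% | 44.6% | 2.3 to 2.8 |
| 40% | 42.3% | 48.1% | 47.1% | 4.9 to 5.8 |
| 60% | 42.3% | 51.3% | 49.9% | 7.7 to 9.0 |

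With equal u and the event-date version, both arms' hazards are multiplied by the same 1 − G(t), so the hazard ratio stays at 0.775. With unequal u it becomes 0.775 × (1 − G_daily)/(1 − G_on/off). With 30% on/off and 15% daily, that is 0.775 × 0.85/0.70 = 0.94 by Week 96.

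**Harder case: confounded starts, with IPCW applied.** Simulation of 400,000 per arm: one measured binary factor triples both the event hazard and the AMX0035 start hazard, controls are calibrated to 65% at Week 48, and weights are saturated by arm, factor and week. Uptake is the nominal probability of starting by Week 96 if no event intervened; at a nominal 40%, 26% to 29% actually started before an event. The true hazard ratio is slightly above 0.775 because the prognostic factor is omitted from the marginal Cox model. Ranges span the two possible censoring dates.

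| Uptake on/off, daily | Control Week 96: truth | Literal + IPCW | HR: truth | Literal + IPCW |
|---|---|---|---|---|
| 10%, 10% | 0.443 | 0.456–0.461 | 0.790 | 0.786–0.787 |
| 20%, 20% | 0.445 | 0.473–0.483 | 0.794 | 0.788–0.791 |
| 40%, 40% | 0.444 | 0.508–0.533 | 0.797 | 0.780–0.787 |
| 30%, 15% | 0.444 | 0.489–0.506 | 0.795 | 0.838–0.864 |
| 15%, 30% | 0.444 | 0.464–0.472 | 0.795 | 0.723–0.738 |
| 30%, 15%, no daily effect | 0.443 | 0.487–0.505 | 0.998 | 1.057–1.086 |

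Weighting removes little of the bias: at 40% equal uptake it moves the control estimate from 0.539 to 0.533, or from 0.520 to 0.508. Censoring every starter at start, with IPCW, comes within 0.002 of the truth in every row, for both the curve and the hazard ratio.

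**The case against.** The best defence is that this is loose wording for the usual analysis. SAP 9.2 says that all data are included regardless of AMX0035 use, but excepts the secondary estimand. That speaks of data, not events, and suggests that follow-up after AMX0035 start is dropped. Protocol 17.4.5.1 describes the primary analysis as using data that follow AMX0035 without censoring; the secondary analysis is its natural counterpart. The last-visit rule was written for the primary endpoint, and no passage expressly carries it over to event-free starters. IPCW and the stated target both fit censoring at initiation, and SAP 9.2.1.3 may say exactly that.

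Much of this stands. A reader might infer that the trial's program censors on the outcome. The documents do not support that, because the operative section cannot be read. What does not fall away is the text itself: SAP 9.2 does not say how the secondary estimand is handled, and Protocol 17.4.5.3 tells the analyst to repeat the primary analysis with only the late event treated differently. A programmer working from the visible sections alone could reasonably build the flawed rule.

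Two limits on size also stand. Uptake appears nowhere in the documents, and use is confined to countries where AMX0035 is commercially available. SAP 4.2 reports 202 subjects enrolled in the extension; a reader might take these as followed to Week 96, but both studies were stopped and the number reaching Week 96 is not given. In a double-blind trial, nothing in the documents suggests unequal uptake.

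**Conclusion.** The concern holds as a defect in the visible wording of Protocol 17.1 and 17.4.5.3 and SAP 3.2.2. Read with the last-visit rule, the wording makes censoring depend on the outcome, and weighting does not repair that.

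Under assumed equal uptake of 20% to 60%, the Week 96 control Kaplan-Meier estimate is about 2 to 9 percentage points too high. A reader might infer that the treatment comparison is also distorted. With equal uptake it hardly is: the hazard ratio moved by less than 0.02. It shifts by roughly 0.04 to 0.09 only when uptake in one arm is assumed to be twice that in the other.

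The analysis is supportive. The primary treatment-policy analysis and the 70% power figure are untouched. All sizes rest on assumed uptake, assumed start times and, in the second simulation, a single measured confounder.

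**What to change.** In Protocol 17.1 and 17.4.5.3 and SAP 3.2.2, state that every subject who starts AMX0035 before an event is censored at the start date, whether or not an event follows, and that the IPCW weights model time to AMX0035 start. Check SAP 9.2.1.3 first. If it already says this, align the other sections with it; if not, correct it too.

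The cost is one sentence in each place. No new data are needed: Protocol 11.1 and 11.3 already require AMX0035 use to be recorded. The change should be settled before the interim lock.
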